- In this epistemological position this study is best regarded as a well powered but exploratory test of the methods contributing a substantial, but tentative, body of new knowledge.
- The data are largely quantitative and the approach largely statistical within a statistical tradition of (Abelson, 1995; Spiegelhalter, 2019). We also follow the principles of (Wagenmakers et al., 2021, 'Seven steps toward more transparency in statistical practice') specifically:
 - (1) visualizing data;
 - (2) quantifying inferential uncertainty;
 - (3) assessing data preprocessing choices;
 - (4) reporting multiple models;
 - (6) interpreting results modestly; and
 - (7) sharing data and code.

Their fifth step, involving multiple analysts is beyond our resources but we welcome offers from others to reanalyse our data, ideally in collaboration but of course our making the data and code available publicly makes it possible for anyone to reanalyse our data. Particular reference to these steps are noted against particular aspects of our analyses below.

- Some elements are frankly exploratory and pathfinding: mainly the quantitative and qualitative data from the "What's Going On?" (WGO, see registration and protocol) and their relationship with other variables. We are particularly careful to present these as such and not to overclaim for them (Wagenmakers et al., 2021, steps 1, 2, 4 and 6).
- In general the statistical position is descriptive and based on estimation rather than formal null hypothesis significance testing (NHST) and we use confidence intervals (CIs) to understand the probable impacts of sample size on precision of estimation of population parameters. Where statistical tests are used, they aim to give a pragmatic indication that non-random effects exist, not to give strong assertions that "x is a statistically significant effect" but, with the CIs, to help disentangle seemingly systematic effects from random ones. (Wagenmakers et al., 2021, steps 2, and 6)
- We recognise that the sample is not a random one so caution will be exercised in any generalisations to the wider population (Wagenmakers et al., 2021, steps 2 and 6).
- We recognise that there will be incomplete responding and that a small proportion of participants may cross from one baseline group, i.e. students or non-students, to the other group. The impacts of these issues will be explored (Wagenmakers et al., 2021, steps 2, 3, 4 and 6).

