This raises the question whether there are simple analyses that throw more appropriate light on the psychometrics of using the questionnaires to measure individual change than do the conventional explorations of psychometric quality of multi-item questionnaire measures for cross-sectional comparisons between people. This will be explored (details in the PPDAC "A" section: analyses, below).

- iii. As most existing data on the well-being and mental health problems of this age group are from student samples, a primary focus will be on differences between a student and a non-student sample both at baseline and subsequently through the year.
- iv. How much do scores on the dependent measures (CORE-OM, EQ-5D-3L and EQ-VAS, see registration) vary across the seven time points and is there evidence that the level of variation varies across the sample, i.e. that temporal stability is not a consistent parameter but show strong individual differences? Analyses of the CORE-OM will consider the non-risk and risk scores only (but see "supplementary analyses").
- v. Does baseline group, student vs. non-student, appear to relate to the dependent variables? Do other demographic predictors relate to the dependent variables? Recognising that "the dependent variables" will have temporal variation this will be divided into two sets of analyses:
 - 1. Using baseline scores only
 - 2. Analysing the full change data (more details below):
 - a. Testing for difference in any systematic linear trend over the seven time points.
 - b. Against within-participant SD of the scores.
 - c. Against highest and lowest within-participant difference from baseline.
- vi. What levels of and changes in stressors/life events (LE) do participants report on the novel "What's going on?" (WGO) measure?
- vii. Is there evidence of systematic relationship between stress and dependent variable scores within-participant over time?
- viii. Given the inevitably non-random nature of the sampling creating the dataset this will be compared with the most recently available census data

from Quito for this age group to see how much the sample differs from the census data where comparable variables are present in the census data.

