 - With hindsight and having conducted analyses along these lines we are aware that there are many other ways of exploring these complexities in survey data and would particularly welcome offers from data analysts to explore other methods of exploration of these issues in this baseline dataset.
 - Baseline non-participation will be reported to the extent that the opportunistic recruitment process allows though this can only be in terms of potential number of students who might have opted into the study and then in terms of the numbers who start the online data collection but opt out before giving usable data.
 - For the CORE-OM and EQ-5D-3L internal reliability and factor analysis will be conducted (but not expecting neat factor structures). In addition, convergent validity correlations between the two measures, and with the EQ-VAS, will be reported, as usual with 95% CIs.
 - Distributions of CORE-OM, EQ-5D-3L and EQ-VAS scores and of WGO scores will be reported with CIs for centiles.
 - Baseline associations between those three dependent variables and the WGO scores will be reported with scattergrams and smoothed LOESS

regression lines and CIs.

- **Change analyses**

- Patterns of post-baseline missingness will be reported. These will almost certainly show a preponderance of simple attrition: i.e. increasing non-response in waves 2 to 7, however, other patterns are also likely to be observed. As there are 64 possible further completion patterns (2^6) the missingness will be analysed in terms of simple dichotomy of "all completed" versus "at least one missing" and in terms of the total number of completions (1 to 7). These will be analysed against baseline demographic and dependent variable scores for evidence of any of these variables showing systematic associations with missingness. The associations will be reported testing against an alpha of .01 as in the baseline analyses but also with CIs for the associations.

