- One key focus is on how much scores on the three dependent measures, CORE-OM, EQ-5D-3L and EQ-VAS vary across the seven time points and particularly the question of whether that variation over time appears to vary systematically across individuals, i.e. that the within individual variance is not compatible with a null model of a shared population parameter showing only random individual differences? As is common in such studies (e.g., Cooper & McConville, 1990; McConville & Cooper, 1996; Murray et al., 2002) the within-participant standard deviation of the scores, "wpSD" across the seven assessment points will be reported and its distribution (histogram with individual points) plotted. The Levene test, an extension of the Bartlett test, will be used to test for heteroscedasticity, i.e. that null hypothesis of that this variance within group (i.e. here participants) is likely to have arisen by sampling vagaries from a shared population value. The Levene is said to give results in which the null hypothesis is rejected at the conventional alpha level of 0.05 more robustly for non-Gaussian distributions than does the Bartlett test.

The wpSD is useful as it is a sensible statistic aggregating change across all occasions. However, in terms of possible implications for liability to gain from help, the aggregation across all measure completions risk hiding particularly high peak scores so two other within-participant change summary indices will be computed:

- Signed maximum change from baseline score ("wpMaxChange").
- Absolute maximum difference between any two completed scores ("wpScoreRange").

These don't allow a formal test for homogeneity of change across participants but they do throw light on possible "spike" and "trough" changes.

All three within-participant summary indices will be positively correlated with each other and this correlation will be reported and the findings carefully reported as correlated but addressing issues whose differences are of interest.

- As noted, the baseline psychometric analyses, while useful guides to the internal reliability of the multi-item measures for comparisons across individuals at a single measurement occasion. However, the cross-sectional,

conventional test theory underlying that use of the internal reliability does not necessarily fit measurement of change within-participants. This will be explored as follows.

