Some participants will probably change group during the year though these will probably be less numerous than "students-who-also-hold-jobs". Due to the timing of the data collection, students are probably more likely to terminate their courses during the year than are non-students to start a degree. Here again, sensitivity analyses will be conducted recomputing the analyses (a) omitting participants who change group at any point in the year and (b) omitting only those changing group whose change comes less than half way through the year and (c) reallocating those who change group to the group they fall in for more than half the year. However, the expectation is that the numbers changing group will be small and the impacts on the ITT findings small or negligible.

Recognising that these dependent variables have temporal variation and this variation is likely to be complexly patterned across the entire sample, the following analyses will be reported for the ITT baseline group comparison and the sensitivity analyses noted above.

- Group difference against mean scores across all non-missing scores from all seven occasions. This extends the analyses of baseline group differences and entirely ignores change over time.
- Group difference in linear trend over the time points using multi-level modelling (MLM). This allows a trend to be fitted both as a fixed effect whose interaction with predictors can be tested, i.e. assuming a single within-group population mean, and then also allowing a free effect, i.e. allowing that linear trend against time may vary between individuals. The MLM provides an individual (free) linear slope if scores at least two time points exist. However, sensitivity checks on effects of missingness will be added by restricting to sequentially larger numbers of time points.
- Group differences in within-participant SD of the scores (wpSD).
- Group differences in within-participant score difference from baseline (wpMaxChange).
- Group differences in within-participant score range (wpScoreRange).
- Do other demographic predictors relate to the dependent variables? Same methods as for group differences.

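### The plan tests and plots within-person variability but never estimates, with a CI, how much true variability differs between people

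*SAP*

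**What the plan says.** Specific question iv (SAP, PPDAC approach) asks how much scores "vary across the seven time points and is there evidence that the level of variation varies across the sample", and explains this as whether "temporal stability is not a consistent parameter but show strong individual differences". The Change analyses section gives the topic prominence and restates it as whether within-person variance is "not compatible with a null model of a shared population parameter showing only random individual differences".

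The planned answer has three parts:
- wpSD, which "across the seven assessment points will be reported and its distribution (histogram with individual points) plotted";
- a Levene test at 0.05 with the participant as the group (centring on mean or median is not stated);
- two further indices, signed maximum change from baseline and score range, which the SAP itself says cannot formally test homogeneity.

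Later in the same section wpSD is compared between students and non-students and across other predictors. No weighting or adjustment for number of completions is given there. Attrition is expected, as "increasing non-response in waves 2 to 7".

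The Epistemological and methodological position section sets the general rule: "In general the statistical position is descriptive and based on estimation rather than formal null hypothesis significance testing".

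**The concern.** Question iv has a size in it, and none of the planned outputs measures that size. A homogeneity test speaks only to whether the true spread is exactly zero. A histogram of raw wpSD shows true spread plus the sampling error of an SD computed from at most seven scores, and pooling people with different numbers of completions widens it further.

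The other longitudinal analyses do not fill the gap. Random slopes describe individual trend, and the intraclass correlation describes overall stability. Neither says how much stability varies from person to person.

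At stake is the answer to one of the study's leading questions. A reader given a p value and a wide histogram cannot tell absent, weak and substantial differences apart, and there is no interval to help.

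**Working it through.** **Inputs.** From the SAP: at most seven occasions, between one and seven completions per person, a null of one shared within-person variance, and Levene at 0.05. Not in the SAP and therefore assumed: number of participants N, completion mix, true spread. The closed-form results take scores as normal and independent within person.

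**The plan's own figure.** The SAP gives no precision for wpSD. Its only precision figure for seven occasions is the 95% interval of 0.0 to .92 for a within-participant alpha of .6 with 28 items. The F interval, 1 − (1 − 0.6)·F with 6 and 6 × 27 = 162 df, gives 0.005 to 0.918, so that figure reproduces.

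**Step 1: spread of wpSD when nobody differs.** For k scores with shared SD σ, wpSD = σ·√(χ²(k−1)/(k−1)).

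| k | central 95%, in units of σ | 90th/10th ratio |
|---|---|---|
| 7 | 0.45 to 1.55 (3.4-fold) | 1.332/0.606 = 2.2 |
| 5 | 0.35 to 1.67 (4.8-fold) | 1.395/0.516 = 2.7 |
| 4 | 0.27 to 1.77 (6.6-fold) | 1.444/0.441 = 3.3 |
| 3 | 0.16 to 1.92 (12-fold) | 1.517/0.325 = 4.7 |

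In an assumed mix (40% with seven scores, 20% each with five, three and two) the ratio is 3.7 with no true differences at all.

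**Step 2: add a true spread.** Let the log of the true SD vary between people with standard deviation w.
- At w = 0.15 the true 90th/10th ratio is exp(2 × 1.2816 × 0.15) = 1.47. The observed ratio at seven scores is 2.4, against 2.2 at w = 0.
- At w = 0.30 the observed ratio at seven scores is 3.0. That is below the 3.7 from the assumed mix with w = 0.

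**Step 3: share of noise.** The sampling variance of log wpSD is v = ¼·trigamma((k−1)/2). At k = 7, v = 0.3949/4 = 0.0987; at k = 4, v = 0.9348/4 = 0.2337. The share of the observed variance that is real is w²/(w² + v).
- w = 0.15: 0.0225/0.1212 = 0.19 at seven scores; 0.0225/0.2562 = 0.09 at four.
- w = 0.40: 0.16/0.2587 = 0.62 at seven scores.
- Noise is exactly half when w = √v, which is 0.31 at seven scores and 0.48 at four.

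**Step 4: the planned test.** Simulated rejection rates for Levene at 0.05, seven scores each, assumed N = 300:

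| True spread w | mean-centred | median-centred |
|---|---|---|
| 0 | about 60% | 0% |
| 0.15 | over 99% | about 1% or fewer |

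The same small spread gives opposite answers according to an unstated option. The mean-centred form also rejects often when there is nothing to find.

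**Step 5: group comparison.** The expected wpSD is c4·σ, with c4 = 0.798 at two scores and 0.959 at seven. Since 0.798/0.959 = 0.83, someone with two scores has an expected wpSD 17% lower than someone with seven at the same true SD. Precision differs too: the coefficient of variation is 0.76 against 0.29.

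**The case against.** The best defence is that the operational question in the Change analyses is yes or no, that a homogeneity test addresses it, and that the authors plainly know some spread is chance, because they name the shared-parameter null and pair the histogram with a test. This stands as far as it goes. It does not supply a size, which question iv asks for and which the SAP's preference for estimation would lead a reader to expect.

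Three stronger readings are tempting and are not supported:

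- *The histogram is mostly noise.* That is conditional. At seven scores it fails once w exceeds about 0.31, and the document gives nothing from which to place w.
- *Weak or absent differences will be reported as strong.* The SAP says tests are only pragmatic indications and commits to modest interpretation, so misreporting cannot be presumed.
- *The test will come out significant on trivial differences.* That follows for mean centring. With median centring the test would almost never reject at w = 0.15.

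Missingness is also partly handled. Number of completions is analysed as an outcome, and the multilevel slope analysis is repeated on people with progressively more time points. As written, that restriction applies to the slopes and not to wpSD. The absence of weighting in the wpSD comparison is read from silence. If groups do not differ in completions, the cost there is mainly lost efficiency.

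Finally, making one particular model the headline for every score would be a matter of preference. Reporting some noise-corrected estimate with an interval is not.

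**Conclusion.** The point holds as a gap in estimation. The plan has no estimate with a CI of the true between-person spread in variability, and no reference showing how much spread chance alone produces. At seven scores the histogram moves only from a ratio of 2.2 to 2.4 between no true differences and a small spread, so it cannot separate the two. The Levene result ranges from about 1% or fewer to over 99% rejection at that same spread, according to its centring.

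The closed-form figures rest on normal, independent scores. In null simulations with 300 people and seven scores, autocorrelation of 0.4 or 0.7 and skewed scores gave coefficients of variation for wpSD of about 0.33 and 0.39, against 0.29 in the normal independent case, so the noise is not overstated. N, the completion mix and w are assumptions. The change is worth making, but it does not invalidate the planned analyses.

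**What to change.** In the wpSD paragraph of the Change analyses, keep the test, state its centring, and add:

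1. On the wpSD histogram, an overlay of the distribution expected under one shared SD at the observed numbers of completions.
2. For CORE-OM-NR and EQ-VAS, an estimate with a 95% CI of the between-person SD of log within-person SD, with sampling noise removed by number of completions. One route subtracts the known sampling mean and variance of log wpSD at each k. In a check with 300 people and mixed completions of three or more, this gave medians of 0.147 and 0.292 for true values of 0.15 and 0.30, and near 0 for 0. A mixed-effects location-scale model is another option.

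Where wpSD is compared between groups and across other predictors, account for number of completions, either by weighting or by putting the predictor in the scale part of such a model.

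The cost is DAP wording and one extra R analysis on data already collected. Version 2.2 predates any inspection of the change data, and the DAP provides for marked amendments when a better method is found. If those data have since been inspected, label the addition accordingly. The downside is a distributional assumption for the residuals, weakest for the risk score and EQ-5D-3L, which is why the estimate is proposed for the other two scores.

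### wpScoreRange grows with the number of waves completed, yet it is compared between students and non-students without conditioning on that number, so unequal drop-out would look like unequal volatility

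*SAP*

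**What the plan says.** SAP, section A (Analyses), Change analyses, adds two indices to the within-participant SD (wpSD). wpScoreRange is the "Absolute maximum difference between any two completed scores"; wpMaxChange is the "Signed maximum change from baseline score". The list of group comparisons later in that section includes "Group differences in within-participant score range (wpScoreRange", with no covariate, stratum or minimum number of completions. Other demographic predictors follow by reference: "Same methods as for group differences".

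The same section expects attrition over waves 2 to 7 and lets the number of completions run from 1 to 7. It uses completion pattern and count only as something to be explained: "These will be analysed against baseline demographic and dependent variable scores". The one missingness check in the group comparisons is that "sensitivity checks on effects of missingness will be added by restricting to sequentially larger numbers of time points"; it stands in the multilevel-model bullet on linear trend. The sensitivity analyses that cover the whole list concern students with jobs and participants who change group. The section on epistemological and methodological position says in general that the effects of incomplete responding will be explored, but names no method.

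**The concern.** A range is a maximum over pairs of scores. A participant with seven waves contributes 21 pairs; one with two waves contributes a single pair. The first will show the larger range on average even if both are equally volatile. A comparison that ignores k therefore mixes two quantities: how much people vary and how often they responded.

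The Problem section makes the student versus non-student contrast a primary focus. If either group leaves the study faster, that group will appear steadier. The SAP's preference for estimation over testing does not protect it, because the estimate itself is displaced and the interval with it. The same holds for any demographic predictor related to drop-out.

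wpMaxChange may share the problem, depending on what it means. The Change analyses call it a signed maximum, whereas question v of the Problem section refers to "Against highest and lowest within-participant difference from baseline". If it is the highest (or lowest) change, its mean moves with k. If it is the largest absolute change with its sign kept, its mean does not move in the absence of drift. The SAP's interest in peak scores and its statement that "All three within-participant summary indices will be positively correlated with each other" fit the highest-change reading: with symmetric scores and no drift, the sign-kept version has zero correlation with range and SD.

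**Working it through.** **The plan's own count.** Seven occasions give C(7,2) = 21 pairs, as the SAP states for test-retest intervals. It gives no retention rate, sample size or power for this comparison, so there is nothing further to reproduce. Everything below on retention, group size and score distribution is an assumption.

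**Step 1: expected range by k.** For k independent normal scores with within-person SD σ, E[R_k] = σ ∫ (1 − Φ(x)^k − (1 − Φ(x))^k) dx.

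| k | 2 | 3 | 4 | 5 | 6 | 7 |
|---|---|---|---|---|---|---|
| E[R_k]/σ | 1.128 | 1.693 | 2.059 | 2.326 | 2.534 | 2.704 |

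A two-wave participant shows 1.128/2.704 = 42% of a full completer's range at equal volatility. Autocorrelation does not remove the gradient: with AR(1) 0.6 the values run from 0.71 to 2.16. The direction needs no distributional assumption; only the size does.

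**Step 2: bias in the group difference.** With constant per-wave retention r and monotone drop-out, among those with k of at least 2, P(k) = r^(k−2)(1 − r) for k = 2 to 6 and P(7) = r^5.

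| k | 2 | 3 | 4 | 5 | 6 | 7 | mean k |
|---|---|---|---|---|---|---|---|
| r = 0.92 | 0.080 | 0.074 | 0.068 | 0.062 | 0.057 | 0.659 | 5.9 |
| r = 0.85 | 0.150 | 0.128 | 0.108 | 0.092 | 0.078 | 0.444 | 5.2 |

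Weighting step 1 by these:
- r = 0.92: 0.090 + 0.125 + 0.139 + 0.145 + 0.145 + 1.782 = 2.43σ
- r = 0.85: 0.169 + 0.216 + 0.223 + 0.214 + 0.198 + 1.200 = 2.22σ

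The spurious difference is 0.21σ. At 90% against 87% it is 2.36 − 2.28 = 0.09σ (from unrounded values).

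**Step 3: false rejection.** Simulation with no true difference, Welch t-test at 5%, 200 per group, 92% against 85%. Individual SDs are log-normal; the columns give the SD of log-volatility.

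| | 0 | 0.3 | 0.5 |
|---|---|---|---|
| Standardised difference, independent occasions | 0.21 | 0.16 | 0.12 |
| Rejection, independent occasions | 49% | 33% | 21% |
| Rejection, AR(1) 0.5 | 57% | 42% | 28% |

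At log-SD 0.3, 100 or 300 per group gives 19% or 48%. Equal retention gives 5%, and 90% against 87% gives 9%. A separate set of drop-out hazards (one shared SD, 100 or 200 per group) gave 14% and 21% for 8% against 12% per wave, and 39% and 68% for 10% against 20%.

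**Step 4: the other indices**, same retention and group size. wpMaxChange gives 15–20% if it is the highest change (expected value 0.00 to 1.27σ for k = 2 to 7) and 5–7% if it is the sign-kept change. wpSD gives 6–8% with independent occasions and 10–17% with AR(1) 0.5.

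**Step 5: the remedy.** With k as a factor, rejection for the range is 4.8–5.2% (independent occasions) and 4.8–5.9% (AR(1) 0.5). In seven-wave completers it is 4.8–5.9% and 4.3–6.5%. With intermittent missingness and autocorrelation, k as a factor still gives about 5%. A minimum of four completions alone leaves 6–19% across the unequal hazards tried.

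**Step 6: its limit.** At log-SD 0.3, let the log-odds of drop-out rise by 0.3 or 0.6 per SD of log-volatility. Rejection is then 41% or 47% unadjusted, 9% or 18% with k as a factor, and 9% or 16% in completers.

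**The case against.** The strongest reply is that the bias depends on a fact the SAP does not assert. Nothing says students and non-students will drop out at different rates, and with a modest gap (90% against 87%) rejection is only about 8–13%. This stands as a limit on size.

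Second, the SAP sets neither a Welch test nor a 5% level for this comparison. It favours intervals, and its screening level for associations is .01, at which the 92% against 85% rates fall to about 27%, 15% and 8%. That is fair about the rejection rates, but the displaced estimate is the same at any level.

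Third, the index is secondary: question v.2 does not list it, it is one of five group comparisons, and wpSD is much less affected. This bears on priority, not on whether the comparison is sound.

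Fourth, the SAP would report unequal completion, and its restriction on time points could be extended to the range. Reporting the imbalance does not correct the index. The restriction is written for the linear slope and, if extended, would leave the main estimate unchanged.

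Finally, k is a post-baseline variable, so conditioning on it is an incomplete cure when drop-out follows volatility, which is plausible for a distress measure. This stands, and the SAP should say so.

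**Conclusion.** The concern holds. Under the SAP as written, any difference in completion between groups passes into the wpScoreRange comparison as an apparent difference in volatility. The mechanism is certain; its size in this study is unknown. Under the assumed 92% against 85% retention it is 0.21 within-person SDs, or a standardised difference of 0.12 to 0.21 depending on how much volatility varies between people. Small imbalances give small artefacts, and equal drop-out gives none. wpMaxChange is affected only if it means the highest or lowest change. This should be fixed, at little cost; it does not undermine the study's other comparisons.

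**What to change.** In the group-comparison list under Change analyses:

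- Require at least two completed waves for the within-participant indices.
- Include k as a categorical factor in every group and demographic comparison of wpScoreRange and wpMaxChange, and of wpSD for consistency.
- Report the seven-completion subset as a sensitivity analysis.
- Give wpMaxChange one definition, reconciling question v with the Change analyses.
- State that both approaches assume drop-out is unrelated to volatility, given k and group.

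The cost is wording and one model term. Intervals could widen slightly if k is closely tied to group, but in the simulated case the standard error did not rise (0.126 with k, 0.135 without). The completer subset is smaller: 200 × 0.92^6 ≈ 121 and 200 × 0.85^6 ≈ 75 under the assumed retention. The SAP provides for marked amendments that correct errors, and this version is dated before any inspection of the change data.

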- That still looks for some shared change across individuals. Dropping that measurement expectation entirely, but transferring CTT to within-participant change allows computation of the alpha for change within-participant. The parametric 95% confidence interval for an observed alpha of .6 from $n = 7$ (i.e. all seven occasions) for 28 items (the CORE-OM-NR) is from 0.0 to .92, i.e. reaching a point at which a model of no reliability of within-participant change is looking implausible. We will report within-participant Cronbach alpha values for all participants with full item data from all seven occasions for the CORE-OM-NR score and also, separately, for those with fewer occasions. Where the parametric lower confidence interval exceeds zero the first principal components of the within-participant PCA will be inspected and it is expected that these will be markedly different for different participants with these high personal change Cronbach alpha values, illustrating that within-participant change on a measure like the CORE-OM can be reliable be markedly different in structure between individuals. This can also be done for all 34 items making up the full CORE-OM. For the shorter scales/scores such as the EQ-5D-3L or the domain scores of the CORE-OM the number of items are not sufficient to give any reasonable power to find internal reliability with only seven measurement occasions and this model will not be explored for the shorter scales/scores.
- Does baseline group, student vs. non-student, appear to relate to change on the dependent variables? All change scores and distributions will be plotted allowing both individual values and central location statistics with CIs to be seen.
All analyses will be firstly "intention to treat" (ITT), i.e. by baseline group.

However, many students will also hold jobs. How much this relates to scores on dependent variables will be explored by analysing with these "students-who-also-hold-jobs" as a group and by reclassifying them into the non-student group. These additional explorations will explore the sensitivity of any relationships to baseline group to these real world complexities.

It seems plausible that these "students-who-also-hold-jobs" are sufficiently different from either the students without any outside course employment or from the young people with jobs and no university study that this issue may need to be considered alongside the simple ITT analyses.

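### Choosing participants by a 95% lower limit for their own alpha, with no chance benchmark, does not separate reliable person-specific change from noise

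*SAP*

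**What the plan says.** The rule is in the SAP, PPDAC approach, A (Analyses), Change analyses, in the item on alpha for change within participants.

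- **Who is tested:** "We will report within-participant Cronbach alpha values for all participants with full item data from all seven occasions" on the CORE-OM-NR score, and separately those with fewer occasions. The analysis may be repeated: "This can also be done for all 34 items making up the full CORE-OM".
- **Calibration:** "The parametric 95% confidence interval for an observed alpha of .6" with seven occasions "for 28 items (the CORE-OM-NR) is from 0.0 to .92". The SAP takes this as the point where no reliability starts to look implausible.
- **Trigger:** "Where the parametric lower confidence interval exceeds zero the first principal components of the within-participant PCA will be inspected".
- **Reading:** the components are expected to differ markedly between the people selected, "illustrating that within-participant change on a measure like the CORE-OM can be reliable be markedly different in structure between individuals".

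The item makes no allowance for the number of participants tested. It plans no comparison of the number selected with the number expected by chance, and it gives no reference for how dissimilar components would look under noise. Elsewhere (Baseline analyses, and the missingness item of Change analyses) the SAP uses an alpha of .01, and under Baseline analyses it explains this by multiple testing.

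**The concern.** A two-sided 95% interval for one pre-chosen participant has a 2.5% chance of lying wholly above zero when that person's true alpha is zero. The SAP applies it to everyone with enough data and then looks only at those who pass. Some will pass by chance, and the more people are tested the more will do so.

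The second step does not filter them out. The first component of seven noisy occasions on 28 items points in an essentially arbitrary direction, so people selected by chance will also show different structures. Noise can thus produce both halves of the expected picture: high personal alphas and differing components.

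At stake is the SAP's only fully person-specific answer to its question (ii), on the quality of the measures for intra-individual change. Followed as written, the plan could present chance selections as reliable change with individual structure.

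**Working it through.** **Inputs from the SAP.** Interval level 95%; observed alpha .6; n = 7 occasions; k = 28 items; selection when the lower limit is above zero. **Assumption.** The number tested, N, is not in the SAP, so a range is shown.

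**1. The SAP's own interval.** The Feldt interval is 1 - (1 - a) x F, with n - 1 = 6 and (n - 1)(k - 1) = 6 x 27 = 162 degrees of freedom.

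- Lower: 1 - 0.4 x F(.975) = 1 - 0.4 x 2.487 = .005
- Upper: 1 - 0.4 x F(.025) = 1 - 0.4 x 0.2045 = .918

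This agrees with the stated 0.0 to .92.

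**2. What the rule selects.** The lower limit exceeds zero when a > 1 - 1/2.487 = .598. The threshold is .656 at five occasions and .747 at three. At each, the chance of selection is 2.5% when true alpha is zero.

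**3. Check of the 2.5% by simulation** (40,000 participants, 28 items, no shared change, seven occasions). The rate was 2.5% with normal items, 2.5% with unequal variances and 2.5% with ordinal 0-4 items. With serially correlated items (AR(1), independent between items; 60,000 participants) it was 3.1% at .3, 4.1% at .5 and 5.5% at .7.

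**4. Selections from noise alone.** With p = .025:

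- expected number = .025 x N
- P(at least one) = 1 - .975^N
- P(at least two) = 1 - .975^N - N x .025 x .975^(N-1)

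| N tested | Expected | At least one | At least two |
|---|---|---|---|
| 20 | 0.5 | 40% | 9% |
| 40 | 1.0 | 64% | 26% |
| 50 | 1.25 | 72% | 36% |
| 100 | 2.5 | 92% | 72% |
| 200 | 5.0 | 99.4% | 96% |
| 300 | 7.5 | 99.95% | 99.6% |

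For example, at N = 40: 1 - .363 - .373 = .264. At least two people are needed before structures can be contrasted.

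**5. Do components of noise-selected people differ?** Yes. The mean absolute cosine between their first components was .19, and it stayed at .19 to .20 with serial correlation. If instead everyone shared one structure, the mean absolute cosine among those selected was .32, .49, .63 and .80 at inter-item correlations of .1, .2, .3 and .5.

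**6. Would the proportion selected be informative?** Yes, once it is set against the null. The chance of selection is P(F > 2.487 x (1 - true alpha)), which gives 11%, 29%, 43%, 61% and 81% at true alphas of .3, .5, .6, .7 and .8.

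**The case against.** The SAP can fairly be defended on several grounds.

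- **Framing.** Change analyses calls these methods new and says that seven occasions give the second one very little power. The section on epistemological and methodological position calls the study exploratory and commits to modest interpretation. This limits the harm but does not supply a benchmark. Low power also makes chance selections a larger share of those selected.
- **Reporting.** Personal alphas are reported for all participants with full data, and separately for those with fewer occasions, so a reader could compare the selected share with 2.5%. This stands as a real safeguard, but the SAP does not plan the comparison.
- **Operation.** The limit triggers an inspection. It does not formally classify anyone as reliable or unreliable. That is right, and the criticism falls on the sentence that reads the selected cases as illustrating reliability.

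A reader might also infer two stronger things. One is that noise will almost surely produce the picture. That depends on N, which the SAP does not state and which the attrition it expects will reduce. It is fair from roughly 150 to 200 participants (89% and 96% for at least two) but not at 40 (26%). Participants with fewer occasions and the optional 34-item repeat would raise the number of tests. The other is that the illustration cannot fail. It can: a strong structure shared by all would give similar components (mean absolute cosine about .8 at an inter-item correlation of .5) and contradict the stated expectation. Weak shared structure, however, would still look different between people.

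**Conclusion.** The point holds in a limited form. The selection step is an uncorrected test at 2.5% per participant, or about 4% to 5.5% if items are serially correlated at .5 to .7. Neither the number selected nor the dissimilarity of components is set against what noise gives. The display therefore does not distinguish reliable person-specific change from chance. How often noise alone would produce it runs from about one in four at N = 40 to nearly always at N = 200, for two or more people. These figures assume independent participants and a per-person rate of 2.5%. The values of N and the size of any serial correlation are assumptions, not figures from the SAP.

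Severity is modest. No group comparison, multi-level model, variability index, reliable-change count or cross-lagged result depends on this step.

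**What to change.** Amend the item on within-participant alpha as follows.

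1. State the number of participants tested. Report the number and proportion selected with a Wilson 95% CI (already the SAP's method for proportions) and the full distribution of personal alphas, separately by number of occasions.
2. Put the number expected by chance, 0.025 x N, beside the number selected.
3. Add a sensitivity reference simulated with no shared change but with item serial correlation over a plausible range, for example AR(1) from 0 to .7. Shuffling occasions independently for each item is not enough, because it removes serial correlation and leaves the reference at 2.5%. If the true null rate were 4.2% or 5.6%, requiring the Wilson interval to lie above 2.5% would declare reliable change in 24% or 49% of pure-noise cohorts at N = 100, and in 49% or 86% at N = 300.
4. State that change is reliable in some participants only if the proportion selected clearly exceeds that reference range, and judge component dissimilarity against the same null. Otherwise present the PCA as description and remove the statement that it illustrates reliable change.

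The cost is a dated SAP amendment and a short simulation script, with no new data. The downside is that the illustration may prove unsupportable if the proportion selected lies within the reference range.
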